5.2.1. Derivations and Handling of Missing Baseline Data

Definition	Reporting Details
Change from Baseline	= Post-Dose Visit Value – Baseline
Log-Transformed Change from Baseline (Log _e Change)	= Log _e (Visit) – log _e (Baseline).

NOTES:

- Unless otherwise specified, the baseline definitions specified in Section 5.2. Baseline Definitions will be used for derivations for endpoints / parameters.
- Unless otherwise stated, if baseline data is missing no derivation will be performed and will be set to missing.
- The baseline definition will be footnoted on all the change from baseline displays.

5.3. Multicentre Studies

There are no planned adjustments for multiple centres or regions due to the size of the study. Enrolment will be presented by country. For all other analyses, all sites, countries and regions will be pooled.

5.4. Examination of Covariates, Other Strata and Subgroups

There are no planned subgroup analyses to be conducted on this study.

Category	Details
Strata	Not applicable for this study
Covariates	Baseline measure will be included as a covariate

5.5. Multiple Comparisons and Multiplicity

Overall, no adjustments will be made for multiple comparisons or multiplicity across different endpoints.

The process to reduce the false discovery rate for the transcriptomic analyses of mRNA expression is detailed in Section 10.1.3.1.

5.6. Other Considerations for Data Analyses and Data Handling Conventions

Other considerations for data analyses and data handling conventions are outlined in the appendices:

Section	Component
12.1	Appendix 1: Protocol Deviation Management and Definitions for Per Protocol Population
12.2	Appendix 2: Schedule of Activities
12.3	Appendix 3: Assessment Windows
12.4	Appendix 4: Study Phases and Treatment Emergent Adverse Events
12.5	Appendix 5: Data Display Standards & Handling Conventions

Section	Component
12.6	Appendix 6 : Derived and Transformed Data
12.7	Appendix 7 : Reporting Standards for Missing Data
12.8	Appendix 8 : Values of Potential Clinical Importance
12.9	Appendix 9 : Abbreviations & Trademarks
12.10	Appendix 10 : List of Data Displays
12.11	Appendix 11 : Example Mock Shells for Data Displays
12.12	Appendix 12 : NONMEM datafile specification

6. STUDY POPULATION ANALYSES

6.1. Overview of Planned Study Population Analyses

Study population analyses including analyses of participant's disposition, protocol deviations, demographic and baseline characteristics, prior and concomitant medications, and exposure and treatment compliance will be based on GSK Core Data Standards. Details of the planned displays are presented in [Table 2](#) below and [Appendix 10](#): List of Data Displays.

The study population analyses will be based on the Safety population, unless otherwise specified.

6.1.1. Study Population Summary Measure

Population analyses will be presented (summarised in tables and listed) by randomised treatment group only.

Table 2 Overview of Planned Study Population Analyses

Endpoint / Parameter / Display Type	Data Displays Generated		
	Table	Figure	Listing
Subject Disposition			
Subject Disposition for the Subject Conclusion Record	Y		
Treatment Status and Reasons for Discontinuation of Study Treatment	Y		Y
Screen Status and Reason for Screen Failure	Y		Y
Subjects by Country and Site ID	Y		
Reasons for Subject Withdrawal			Y
Subjects for Whom the Treatment Blind was Broken			Y
Planned and Actual Treatments			Y
Protocol Deviations			
Important Protocol Deviations	Y		Y
Subjects with Inclusion/Exclusion Criteria Deviations			Y

Endpoint / Parameter / Display Type	Data Displays Generated		
	Table	Figure	Listing
Populations Analysed			
Study Populations	Y		
Exclusion from Any Population	Y		Y
Demographic and Baseline Characteristics			
Demographic Characteristics	Y		Y
Age Ranges	Y		
Race and Racial Combinations	Y		Y [1]
Ulcerative Colitis Baseline Characteristics [2]	Y		Y
Prior/Current Medical Conditions and Concomitant Medications [3]			
Medical Conditions	Y		Y
Concomitant Medications [4]	Y		Y
Cardiovascular Risk Factors	Y		Y
Exposure and Treatment Compliance			
Exposure to Study Treatment	Y		Y
Study Drug Accountability			Y

NOTES:

- Y = Yes display generated.

1: Listing of race.

2: Baseline characteristics including: Baseline Mucosal Appearance at Endoscopy Mayo Subscore, Baseline Total Mayo Score, Baseline Partial Mayo Score, Baseline 3-domain Mayo Score, Baseline UCEIS Total Score, Baseline Modified Riley Scale, Baseline FCP, Baseline FCP category, Baseline concomitant medications for UC (Glucocorticoids only, Immunosuppressants only, Glucocorticoids and immunosuppressants, No glucocorticoids or immunosuppressants), Baseline Prednisone dose, Family History of Premature Coronary Artery Disease and History of Tobacco Use.

3: Separate summaries for Current and Past Medical Conditions/Cardiovascular Risk Factors/Concomitant Medications.

4: The ingredients of concomitant medications will be reviewed by the clinical and medical team to determine baseline use of Glucocorticoids, Immunosuppressants and Prednisone.

7. SAFETY ANALYSES

The safety analyses will be based on the Safety population, unless otherwise specified.

7.1. Adverse Events Analyses

Adverse events analyses including the analysis of adverse events (AEs), Serious (SAEs) and other significant AEs will be based on GSK Core Data Standards. The details of the planned displays are provided in [Table 3](#) below and [Appendix 12: List of Data Displays](#).

7.1.1. Adverse Event Summary Measures

AE data will be summarised in tables and figures by the following:

- Part A by randomised treatment;
- Parts A, B and follow-up by randomised treatment;
- Parts A, B and follow-up by period treatment (i.e. treatment participant actually received).

AE data will be presented in data listings by the following:

- Parts A, B and follow-up by period treatment (i.e. treatment participant actually received).

Table 3 Overview of Planned Adverse Event Analyses

Endpoint / Parameter/ Display Type	Absolute		
	Summary		Individual
	T	F	L
Adverse Events (AEs)			
All AE by Maximum Intensity by SOC and PT	Y		
All Drug-Related AEs by Maximum Intensity by SOC and PT	Y		
Common ($\geq 10\%$) AEs / Drug-Related AEs by Overall Frequency	Y	Y ^[1]	
Common ($\geq 10\%$) Non-serious AEs by SOC and PT (Number of Subjects and Occurrences)	Y		
All AEs	Y		Y
Subject Numbers for Individual AEs			Y
Relationship Between AE SOCs, PT & Verbatim Text			Y
Serious and Other Significant AEs			
Serious AEs by SOC and PT (Number of Subjects and Occurrences)	Y		
Fatal Serious AEs			Y
Non-Fatal Serious AEs			Y
AEs Leading to Permanent Discontinuation of Study Treatment or Withdrawal from Study	Y		Y
Reasons for Considering as a Serious AE			Y
Possible Suicidality-Related AE (PSRAE)			Y

NOTES:

- T = Table, F = Figures, L = Listings, Y = Yes display generated, SOC = System Organ Class, PT = Preferred Term.
 - Summary = Represents TF related to any summaries (i.e. descriptive statistics) of the observed raw data.
 - Individual = Represents L related to any displays of individual participant observed raw data.
- 1: Plot of common AEs and relative risk will be generated.

7.2. Clinical Laboratory Analyses

Laboratory evaluations including the analyses of Chemistry laboratory tests, Hematology laboratory tests, Urinalysis, and liver function tests will be based on GSK Core Data Standards. [Table 4](#) provides an overview of the planned analyses with further detail being presented in [Appendix 10](#): List of Data Displays.

7.2.1. Clinical Laboratory Summary Measures

Clinical Laboratory data will be summarised in tables and figures by the following:

- Parts A, B and Follow-up by randomised treatment;
- Parts A, B and Follow-up by period treatment (i.e. treatment participant actually received).

Clinical Laboratory data will be presented in data listings by the following:

- Parts A and B and follow-up by period treatment (i.e. treatment participant actually received).

Table 4 Overview of Planned Clinical Laboratory Analyses

Endpoint / Parameter/ Display Type	Absolute			Change from BL		
	Summary		Individual	Summary		Individual
	T	F	L	T	F	L
Chemistry						
Chemistry Results				Y		
Chemistry Lipids Results ^[1]				Y ^[2]		
Worst Case Chemistry Results Relative to PCI Criteria Post-Baseline Relative to Baseline	Y					
Worst Case Lipids Results Relative to NR Criteria Post-Baseline Relative to Baseline ^[1]	Y					
Lipids Outside of the Normal Range ^[1]			Y			
Hematology						
Hematology Results				Y		
Worst Case Hematology Results Relative to PCI Criteria Post-Baseline Relative to Baseline	Y					

Endpoint / Parameter/ Display Type	Absolute			Change from BL		
	Summary		Individual	Summary		Individual
	T	F	L	T	F	L
Urinalysis						
Urine Concentration				Y		
Worst Case Urinalysis Results (Discrete or Character Values) Post-Baseline Relative to Baseline	Y					
Hepatobiliary (Liver)						
Liver Monitoring/Stopping Event Reporting	Y					
Hepatobiliary Laboratory Abnormalities	Y					
Medical Conditions for Subjects with Liver Stopping Events			Y			
Substance Use for Subjects with Liver Stopping Events			Y			
Scatter Plot of Maximum Versus Baseline for ALT		Y				
Scatter Plot of Maximum ALT Versus Maximum Total Bilirubin		Y				
All Laboratory ^[3]						
All Laboratory Data for Subjects with Any Value of PCI			Y			
Laboratory Data with Character Results			Y			

NOTES:

- T = Table, F = Figures, L = Listings, Y = Yes display generated, PCI = Potential Clinical Importance
- Summary = Represents TF related to any summaries (i.e. descriptive statistics) of the observed raw data.
- Individual = Represents L related to any displays of individual participant observed raw data.

1: Lipids parameters = LDL Cholesterol, HDL Cholesterol, Total Cholesterol, Triglycerides and Cholesterol/HDL ratio

2: Percentage changes from baseline.

3: Chemistry, Hematology and Urinalysis will be considered.

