Study Duration and Dosing	
 Each participant will participate in the study for approximately 20 weeks. This includes a screening period up to 30 days, an 84-day (12 week) treatment period, and a 28-day follow-up period after the last dose. Within 30 days of the screening visit (defined as day of consent signing), eligible participants enter a 2-part treatment phase as follows with study treatment starting on study day 1: 
 Part A: Approximately 36 participants are randomly assigned to receive either GSK2982772 60 mg three times daily (TID) or placebo TID for 42 days (6 weeks) in a 2:1 ratio. Part B: All participants who complete Part A move on to receive open label treatment of GSK2982772 60 mg TID for an additional 42 days (6 weeks). Treatment duration is a total of 84 days (12 weeks) inclusive of Parts A and B. Participants are followed-up for 28 days (4 weeks) after the last dose in Part B. Prior to amendment 01 being effective in each country, participants were randomly assigned to receive either: 
 Part A: GSK2982772 60 mg two times daily (BID) or placebo BID for 42 days (6 weeks) in a 2:1 ratio. Part B: Open label treatment for all participants who have completed Part A of GSK2982772 60 mg BID for an additional 42 days (6 weeks). 																															
Time & Events	
 Refer to Appendix 2: Schedule of Activities. During the 84-day (12 week) treatment period, participants attend the clinical for visits on Days 1, 15, 29, 43, 57, 71 and 85. At specific visits, participants must not take treatment prior to their scheduled treatment. On Days 8, 22, 36, 50, 64 and 78 participants were to be contacted by telephone and asked about their general health. Participants are given a diary card at every visit and asked to record daily study 																															

Overview of Study Design and Key Features	
	medication, concomitant medication and adverse events.

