12.3. Appendix 3: Assessment Windows

12.3.1. Definitions of Assessment Windows for Analyses

No Assessment Windows will be defined for Analysis, and summaries and analyses will be based on nominal visits.

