3.21.	Safety	AE16	Summary of Serious Adverse Events by System Organ Class and Preferred Term (Number of Subjects and Occurrences) (Parts A, B and Follow-up) by Period Treatment	FDAAA, EudraCT	IA SAC [1], SAC [1]
3.22.	Safety	AE1	Summary of Adverse Events Leading to Permanent Discontinuation of Study Treatment or Withdrawal from Study (Part A only) by Randomised Treatment	IDSL	IA SAC [1], SAC [1]
3.23.	Safety	AE1	Summary of Adverse Events Leading to Permanent Discontinuation of Study Treatment or Withdrawal from Study (Parts A, B and Follow-up) by Randomised Treatment	IDSL	IA SAC [1], SAC [1]
3.24.	Safety	AE1	Summary of Adverse Events Leading to Permanent Discontinuation of Study Treatment or Withdrawal from Study (Parts A, B and Follow-up) by Period Treatment	IDSL	IA SAC [1], SAC [1]
Laboratory: Chemistry					
3.25.	Safety	LB1	Summary of Chemistry Changes from Baseline (Parts A, B and Follow-up) by Randomised Treatment	ICH E3	IA SAC [1], SAC [1]
3.26.	Safety	LB1	Summary of Chemistry Changes from Period Baseline (Parts A, B and Follow-up) by Period Treatment	ICH E3	IA SAC [1], SAC [1]
3.27.	Safety	LB1	Summary of Lipids Percentage Changes from Baseline (Parts A, B and Follow-up) by Randomised Treatment	Lipids parameters = LDL Cholesterol, HDL Cholesterol, Total Cholesterol, Triglycerides and Cholesterol/HDL ratio	IA SAC [1], SAC [1]

Safety: Tables					
No.	Population	IDSL / Example Shell	Title	Programming Notes	Deliverable [Priority]
3.28.	Safety	LB1	Summary of Lipids Percentage Changes from Period Baseline (Parts A, B and Follow-up) by Period Treatment	Lipids parameters = LDL Cholesterol, HDL Cholesterol, Total Cholesterol Triglycerides and Cholesterol/HDL ratio	IA SAC[1], SAC [1]
3.29.	Safety	LB17	Summary of Worst Case Chemistry Results by PCI Criteria Post-Baseline Relative to Baseline (Parts A, B and Follow-up) by Randomised Treatment	ICH E3 (i.e. treatment emergent)	IA SAC [1], SAC [1]
3.30.	Safety	LB17	Summary of Worst Case Chemistry Results by PCI Criteria Post-Baseline Relative to Period Baseline (Parts A, B and Follow-up) by Period Treatment	ICH E3 (i.e. treatment emergent)	IA SAC [1], SAC [1]
3.31.	Safety	LB17	Summary of Worst Case Lipids Results by NR Criteria Post-Baseline Relative to Baseline (Parts A, B and Follow-up) by Randomised Treatment	Lipids parameters = LDL Cholesterol, HDL Cholesterol, Total Cholesterol Triglycerides and Cholesterol/HDL ratio	IA SAC [1], SAC [1]

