3.44.	Safety	LIVER10	Summary of Hepatobiliary Laboratory Abnormalities (Parts A, B and Follow-up) by Period Treatment	IDSL	IA SAC [1], SAC [1]
ECGs					
3.45.	Safety	EG1	Summary of ECG Findings (Parts A, B and Follow-up) by Randomised Treatment	IDSL	IA SAC [1], SAC [1]
3.46.	Safety	EG1	Summary of ECG Findings (Parts A, B and Follow-up) by Period Treatment	IDSL	IA SAC [1], SAC [1]
3.47.	Safety	EG10	Summary of Maximum QTc Values Post-Baseline Relative to Baseline by Category (Parts A, B and Follow-up) by Randomised Treatment	IDSL	IA SAC [1], SAC [1]
3.48.	Safety	EG10	Summary of Maximum QTc Values Post-Baseline Relative to Screening by Category (Parts A, B and Follow-up) by Randomised Treatment	Change relative to average of screening triplicates	SAC[1]
3.49.	Safety	EG10	Summary of Maximum QTc Values Post-Baseline Relative to Period Baseline by Category (Parts A, B and Follow-up) by Period Treatment	IDSL	IA SAC [1], SAC [1]
3.50.	Safety	EG2	Summary of Change from Baseline in ECG Values (Parts A, B and Follow-up) by Randomised Treatment	IDSL	IA SAC [1], SAC [1]
3.51.	Safety	EG2	Summary of Change from Screening in ECG Values (Parts A, B and Follow-up) by Randomised Treatment	Change relative to average of screening triplicates	SAC [1]
3.52.	Safety	EG2	Summary of Change from Period Baseline in ECG Values (Parts A, B and Follow-up) by Period Treatment	IDSL	IA SAC [1], SAC [1]
3.53.	Safety	EG11	Summary of Maximum Increase in QTc Values Post-Baseline Relative to Baseline by Category (Parts A, B and Follow-up) by Randomised Treatment	IDSL	IA SAC [1], SAC [1]

Safety: Tables					
No.	Population	IDSL / Example Shell	Title	Programming Notes	Deliverable [Priority]
3.54.	Safety	EG11	Summary of Maximum Increase in QTc Values Post-Baseline Relative to Screening by Category (Parts A, B and Follow-up) by Randomised Treatment	Change relative to average of screening triplicates	SAC [1]
3.55.	Safety	EG11	Summary of Maximum Increase in QTc Values Post-Baseline Relative to Period Baseline by Category (Parts A, B and Follow-up) by Period Treatment	IDSL	IA SAC [1], SAC [1]
Vital Signs					
3.56.	Safety	VS1	Summary of Change from Baseline in Vital Signs (Parts A, B and Follow-up) by Randomised Treatment	ICH E3	IA SAC [1], SAC [1]
3.57.	Safety	VS1	Summary of Change from Period Baseline in Vital Signs (Parts A, B and Follow-up) by Period Treatment	ICH E3	IA SAC [1], SAC [1]

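### The worst-case and maximum laboratory, ECG and vital-sign tables contain no like-for-like comparison of GSK2982772 with placebo

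*SAP*

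**What the plan says.** Laboratory values, vital signs and ECG are primary endpoints (SAP Section 2.2). Sections 7.2.1 and 7.3.1 give them two groupings, both spanning Parts A, B and Follow-up: one by randomised treatment, and one set out as "Parts A, B and Follow-up by period treatment (i.e. treatment participant actually received".

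Section 5.1 maps every active code, double-blind and open-label, to a single GSK2982772 60mg table column. The only other column is Placebo. Section 5.2 sets Day 43 as the period baseline for Part B.

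Section 12.10.5 carries the period grouping into the worst-case and maximum tables, for example "Summary of Worst Case Chemistry Results by PCI Criteria Post-Baseline Relative to Period Baseline (Parts A, B and Follow-up) by Period Treatment" (Table 3.30) and "Summary of Maximum Increase in QTc Values Post-Baseline Relative to Period Baseline by Category (Parts A, B and Follow-up) by Period Treatment" (Table 3.55). Tables 3.32, 3.36, 3.40, 3.49 and 3.59 follow the same pattern. Section 12.3.1 adds that "summaries and analyses will be based on nominal visits".

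For adverse events, Section 7.1.1 also plans a Part A display by randomised treatment. No such display is planned for laboratory, ECG or vital-sign data.

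**The concern.** A worst case or maximum over more visits is more extreme even when treatment does nothing. In the period-treatment tables the drug column collects visits from both parts, while the placebo column collects only Part A. A reader comparing the two columns would see more flagged participants on GSK2982772 for that reason alone.

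The randomised-treatment versions (3.29, 3.31, 3.35, 3.39, 3.47, 3.53, 3.58) balance the number of visits, but they do not isolate placebo: the placebo column there includes open-label drug in Part B. So neither set shows worst-case results for drug against placebo over the same number of visits. The study's primary purpose is safety, and these tables are where isolated abnormal values are summarised.

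There is a secondary point on the by-visit tables grouped by period treatment (3.26, 3.28, 3.34, 3.52, 3.57). Their Day 57, 71 and 85 rows combine people at different times on drug and with different kinds of baseline.

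**Working it through.** **Inputs from the SAP**
- Section 2.3: about 36 participants, "placebo TID for 42 days (6 weeks) in a 2:1 ratio", so 24 drug and 12 placebo. Part A completers then "move on to receive open label treatment of GSK2982772 60 mg TID for an additional 42 days (6 weeks". 42 + 42 = 84 days, which agrees with "Treatment duration is a total of 84 days (12 weeks) inclusive of Parts A and B".
- Section 2.3: clinic "visits on Days 1, 15, 29, 43, 57, 71 and 85". The schedule in Section 12.2.1 places chemistry, haematology, ECG and vital signs at each of these and at Follow-up, 28 days after the last dose. Day 43 is pre-dose and belongs to Part A (Section 12.4.1).
- Section 12.2.1, footnote 13: no urinalysis on Days 29, 57 and 71.
- Section 12.5.2: unscheduled visits stay out of safety summary tables, so only scheduled visits count.

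**Post-baseline visits per completer**
- Drug arm, drug column: Days 15, 29, 43, 57, 71, 85 = 6; with Follow-up 7.
- Switcher, drug column: Days 57, 71, 85 = 3; with Follow-up 4.
- Placebo column: Days 15, 29, 43 = 3.
- Urinalysis, with Follow-up: drug arm 4 (Days 15, 43, 85, Follow-up), switcher 2, placebo 2.

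**Flag rate with no drug effect.** The SAP gives no per-visit rate, so p is assumed. For independent visits and one worst case per participant, P(any flag in k visits) = 1 − (1 − p)^k. At p = 3%: k = 3 gives 8.7%, k = 4 gives 11.5%, k = 6 gives 16.7%, k = 7 gives 19.2%.
- With Follow-up: drug column (24 × 19.2% + 12 × 11.5%)/36 = 16.6%; placebo 8.7%; ratio 1.9. That is about 6 of 36 against 1 of 12.
- Without Follow-up: (24 × 16.7% + 12 × 8.7%)/36 = 14.0%; ratio 1.6.
- For p from 1% to 5%, with Follow-up, the ratio runs from 2.0 to 1.8.

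**Correlated visits.** Simulating a latent normal variable with equal between-visit correlation, p = 3%, Follow-up included:
- correlation 0.5: 12.0% against 7.4%, ratio 1.6;
- correlation 0.9: 6.3% against 5.0%, ratio 1.3.

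**Worst case taken per part.** Part A is 3 visits against 3. Part B plus Follow-up on drug is 4 visits, against 3 on placebo in Part A: 11.5% against 8.7%, ratio 1.3 with independent visits. Without Follow-up the counts are equal.

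**By-visit rows.** Weeks on drug are (day − 1)/7 for the drug arm and (day − 43)/7 for switchers.
- Day 57: weeks 8 and 2.
- Day 71: weeks 10 and 4.
- Day 85: weeks 12 and 6.

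Each row pools 24 with 12 participants. The Day 43 re-baseline means the drug arm's change is measured from a value already on drug. A constant drug effect therefore shows as no change in 24 participants and in full in 12, so the row shows 12/36, or one third, of it.

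**The case against.** The strongest reply has four parts.

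1. The randomised-treatment by-visit tables (3.25, 3.27, 3.33, 3.50, 3.56) compare drug with concurrent placebo on Days 15, 29 and 43, and keep switchers in their own column afterwards. This stands. A reader might infer that the plan offers no clean comparison of these endpoints at all; it does, by visit, up to Day 43. The gap is in the worst-case and maximum tables, and the by-visit mixing is secondary.

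2. Follow-up is off drug, and Section 5.1 lists no period-treatment code for it. This also stands. It would be tempting to say that participants have 7 visits on drug, but the schedule supports 6 in or at the end of treatment. The seventh falls under drug only by inference from the table titles and the two-column layout.

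3. The SAP does not say whether the worst case is taken once per participant or once per part. The period baseline makes per-part derivation plausible. Section 12.6.1 points the other way, with a row covering any post-baseline visit that also applies to the clinical-importance tables. The display shells are not in the document (Section 12.11), so the question stays open, and the smaller imbalance is possible.

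4. The displays are descriptive, with no hypothesis tests (Section 2.4), and listings by period treatment let a reader trace individual values. That limits the harm, but it does not supply the missing summary.

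**Conclusion.** The point holds for the worst-case and maximum tables: no version compares drug with placebo over equal visits with the placebo column free of drug exposure. The visit counts follow directly from the SAP's schedule, assuming full completion.

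The size of the distortion rests on assumptions. A reader might take the near-doubling as the expected bias. That needs one worst case per participant, independent visits and Follow-up counted as drug. Repeated values from one person are usually correlated, which brings the ratio to about 1.3 to 1.6 at the correlations tried. Per-part derivation caps it at about 1.3. The direction, more flags on drug with no drug effect, is the same in all these cases except per-part derivation without Follow-up, where the counts are equal.

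This should be corrected because these are primary endpoints and the correction is cheap. It does not undermine the randomised-treatment by-visit comparison to Day 43.

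**What to change.** - Add Part A-only worst-case and maximum tables by randomised treatment for laboratory, ECG and vital-sign data, following Section 7.1.1 for adverse events, and use these for the comparison with placebo. Each arm then has Days 15, 29 and 43 (urinalysis Days 15 and 43). With no drug effect at 3% per visit, the expected rate is 8.7% in both arms (urinalysis 1 − 0.97² = 5.9% in both).
- In the period-treatment tables, state that the worst case is derived separately for each part. Show drug-arm participants and switchers separately in Part B, by time since first active dose. Report Follow-up as its own off-drug row without a placebo comparison.

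Pooling all participants' weeks 2, 4 and 6 on drug against placebo would be a weaker remedy. Switchers have urinalysis only at week 6, and blinded data would be mixed with open-label data. The same 12 people would also appear in both columns.

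The cost is a few more descriptive tables and some SAP wording. No new data are required.
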